6.2 Secondary Efficacy Estimand Analyses for Main Study

The primary analysis for the secondary estimands with binary endpoints will be based on the ITT population following the same methods as the primary estimand, and reported as described for each estimand including reporting by randomization strata if the interaction term in the GLM used for the primary pivotal analysis plus the interaction term is significant at the 0.05 level. Missing data will be imputed according to Section 4.3.

Binary secondary endpoints include: mortality rate, NIHSS responder and worsening of stroke.

For the secondary estimand of the "mRS shift analysis", the first step in the analysis will be an adjusted analysis with mRS score 5 and 6 combined, using a proportional odds model to derive the common odds of improvement ("shift") along the mRS scale. The mRS shift analysis will

only be conducted provided that the proportional odds assumption is found to be valid on testing. If it is found to be invalid, the remaining secondary endpoints will be deemed to be protected. Adjustment will include the same variables as the primary outcome analysis.

All tests will be conducted with two-sided level of significance alpha = 0.05 (overall for the in trial), adjusted for the interim analysis per the O'Brien-Fleming boundary spending function. A fixed sequence multiple testing procedure will control the overall experiment-wise error rate for the trial (see below). It pre-specifies that, with all tests conducted at the same pre-specified significance level, the primary endpoint will be tested first, and all subsequent tests are considered failed and deemed exploratory if conducted, in the order specified (primary analysis first, key secondary analysis second, etc.), after the first test which fails. All tests that follow the first failed test, are considered exploratory. The secondary endpoints, and the order they are to be tested, are as they are listed in Table 1: Objectives and Endpoints.

Sensitivity analysis of the secondary estimands will be conducted in ITT population with missing data not imputed.

Additional analysis details of each outcome along with the supportive analyses of the secondary estimands are specified in each section below.

6.2.1 Mortality

Mortality rates, defined as the number of deaths observed divided by the number of participants observed over the 90-day study period between nerinetide and placebo control participants. Results will be summarized and tabulated.

In addition to the primary and sensitivity analysis, mortality analysis will be additionally supported using:

- Time-to-death survival function analysis, both unadjusted using Kaplan-Meier analysis and adjusted via Cox proportional hazards regression. Subjects who are known to be alive or the mortality status is unknown at study completion/discontinuation will be censored at the date of completion/discontinuation.
- Unadjusted logistic regression as described for the primary estimand

Mortality status scores will be listed by treatment arm and subject.

6.2.2 Worsening of Stroke

Worsening of Stroke is determined as the number of participants experiencing at least one worsening of stroke divided by the number of participants observed over the 90-day period in that treatment group, between nerinetide and placebo control participants. Results will be summarized and tabulated. The unadjusted logistic regression method will be used as a supportive analysis. The alpha protected secondary analysis of Worsening of Stroke as currently designed will also be supported by a further analysis in which the imaging requirement is waived, in order to include in this supportive analysis any cases in which the stroke worsened so rapidly that the patient was deemed palliative early on and did not undergo further imaging.

6.2.3 Secondary Outcome Analysis – mRS shift analysis

The primary analysis of the ordinal mRS scores will employ a proportional odds model (POM) to test the hypothesis that, among randomized subjects, those who are treated with nerinetide will show a shift in their mRS score distribution at 90 days relative to the mRS distribution of the

placebo subjects. The magnitude of the shift will be estimated as the common odds ratio (95% CI). Modified Rankin scores of 5 and 6 (bed-bound with severe disability, and death) will be collapsed into a single category representing severely limited functioning. An adjusted POM will be used to derive the common odds of improvement (i.e. the nerinetide vs. placebo "shift" in mRS score distributions). Adjustment will include the same variables as the primary outcome analysis. The mRS shift analysis will only be conducted provided that the proportional odds assumption is found to be valid on testing. Deceased participants will be included with a mRS score of 6.

For the purpose of clarity, since the analysis of the ordinal mRS scores will employ a proportional odds model (POM), if test of the proportional odds assumption shows the assumption to be invalid, this key secondary analysis will not be performed and the remaining secondary outcomes will be deemed to be protected.

Example SAS code for POM testing as follows:

```
PROC LOGISTIC DATA=ADMRS;
```

```
CLASS TRTP RANDTIME SEX BASPECT OCCLOC SITEGR1 / PARAM=GLM;
MODEL AVAL = TRTP RANDTIME AGE SEX BNIHSS BASPECT OCCLOC
IMA_TIME SITEGR1;
EFFECTPLOT INTERACTION(X=TRTP SLICDBY=AVAL) / POLYBAR;
ODDSRATIO TRTP / CL=WALD DIFF=ALL;
```

RUN;

Where "AVAL' is the collapsed mRS scale values ranging from 0 to 5 (level 5 = 5+6 mRS combined).

When SAS fits the POM, it runs a global test for a shift across all 6 mRS categories in the nerinetide group relative to the placebo; this is the test of the proportional odds (PO) assumption. The proportional odds assumption will be checked via the score test at an alpha-level of 0.15 and also using graphical methods to view the cumulative log odds for each mRS score. If the assumption holds, the POM estimates a single fixed odds ratio for the 5 cumulative binary endpoints defined as follows:

- 1) The proportion of subjects with mRS = 0 vs. the proportion with mRS > 0
- 2) The proportion of subjects with mRS ≤ 1 vs. the proportion with mRS>1
- 3) The proportion of subjects with mRS ≤ 2 vs. the proportion with mRS>2
- 4) The proportion of subjects with mRS ≤ 3 vs. the proportion with mRS>3
- 5) The proportion of subjects with mRS ≤ 4 vs. the proportion with mRS>4

This means that regardless of how one chooses to dichotomize the mRS scale, the ratio of the odds of a nerinetide-treated subject's being in the higher functioning category of the dichotomy to a control subject's odds, will remain the same over the entire span of the mRS scale. Thus, there is no advantage to estimating ORs singly for any of the above dichotomies. If the PO assumption holds, none of them will be significantly different from the common odds ratio. This is analogous to the proportional hazard assumption of the Cox regression model, which posits a constant ratio of treatment vs. control hazard rates at every time point in a study.

Note that the model tests and estimates associated with endpoints "b" and "c" are the more commonly used (and less efficient) mRS dichotomies that represent "good" vs. "poor" functioning. Thus, in addition to providing a statistically powerful test for a treatment vs. placebo shift across all the mRS scores, the POM subsumes the more common dichotomous mRS analyses that efficacy decisions in stroke trials are often based on (Agresti 2007; Nunn 2016)^{16,17}.

The results of the PO assumption tests, the common odds ratio estimate (with Wald 95% CIs) and corresponding Wald test statistics will be summarized in a table. Actual proportions in each category of the collapsed mRS scale with corresponding stacked bar charts will also be presented.

6.2.4 National Institutes of Health Stroke Scale

The NIHSS scores will be dichotomized into 0-2 (indicating a good neurological outcome) versus >2 (indicating otherwise). The proportion of subjects achieving a good neurological outcome at Day 90 or the last rating after day 30 in nerinetide versus placebo control subjects will be summarized and tabulated.

The same unadjusted logistic regression as discussed for the primary estimand will be used as a supportive analysis.

Baseline, Post EVT, Day 5, Day 30 and Day 90 NIHSS scores will be listed by treatment arm and subject.

6.3 Tertiary Efficacy Outcomes Analyses for Main Study

Summary statistics for each tertiary efficacy endpoint will be tabulated by treatment group. The tertiary analyses will be considered exploratory, and therefore are not subject to the fixed sequence multiple testing procedure to control the overall experiment-wise error rate for the trial as was done for the secondary analyses. These efficacy outcomes will be reported as described for each outcome including reporting by randomization strata if the interaction term in the GLM used for the primary pivotal analysis plus the interaction term is significant at the 0.05 level.

The tertiary efficacy endpoints include the:

- Volume of stroke as measured by MRI or CT brain imaging (MRI preferred).
- Proportion of participants with functional independence in activities of daily living, as defined by a score of ≥ 95 on the Barthel Index (BI) at Day 90 post randomization.
- Proportion of participants with reduced moderate or severe disability or death, as defined by a score of 4-6 on the mRS at Day 90 post randomization.
- Proportion of participants with excellent functional outcome, as defined by a score of 0-1 on the mRS at Day 90 post randomization.
- Health-related quality of life, as measured by the EQ-5D-5L at Day 90.

6.3.1 Volume of Stroke

Total volume will be assessed using an adjusted analysis comprising of a linear regression that includes the stratification and minimization variables, and supported by an unadjusted two-tailed Student's t-test. A cubic root transformation will be performed if needed. Results will be reported with confidence intervals for the unadjusted and adjusted treatment effect between treatment groups.

Stroke volume will be listed by treatment arm and subject.

6.3.2 Barthel Index

The BI scores will be dichotomized at 0-90 (indicating otherwise) versus 95-100 (indicating independent functioning with activities of daily living). The proportion of subjects with independent functioning with activities of daily living at Day 90 in nerinetide versus placebo control subjects will be analyzed using the same method as the primary analysis for the primary estimand. Results will be summarized and tabulated.

Baseline, Day 30 and Day 90 BI scores will be listed by treatment arm and subject.

6.3.3 Proportion of subjects with Day 90 mRS 4-6

The Day 90 mRS score will be dichotomized at mRS \geq 4 (indicating moderate, severe disability or death) vs. mRS < 4 (indicating otherwise). The proportion of subjects with based on this dichotomy on Day 90 in nerinetide versus placebo control subjects will be analyzed as the primary analysis described for the primary estimand. Results will be summarized and tabulated.

6.3.4 Proportion of subjects with Day 90 mRS ≤ 1

The Day 90 mRS score will be dichotomized at mRS≤1 (indicating freedom from disability) vs. mRS>1 (indicating otherwise). The proportion of subjects with freedom from dependence/disability based on this dichotomy on Day 90 in nerinetide versus placebo control subjects will be analyzed using the same method as the primary analysis for the primary estimand. Results will be summarized and tabulated.

6.3.5 EQ-5D-5L

For the EQ-5D-5L, the difference between nerinetide and placebo control subjects in the distribution of the EQ-VAS score at Day 90 will be summarized descriptively and modeled as a continuous variable. An analysis of covariance (ANCOVA) model will be fit to the EQ-VAS endpoint with the nerinetide/placebo treatment indicator variable and the stratification variables and covariates used in the supportive primary and secondary efficacy analyses. ANCOVA results will be summarized in a table. Least squared means, standard error and 95% CI will be reported.

The five dimensions of EQ-5D-5L (Mobility, Self-Care, Usual Activities, Pain/Discomfort, and Anxiety/Depression) will be summarized using frequency counts and percentages separately by treatment group.

Day 90 EQ-5D scores will listed by treatment arm and subject.

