In the Phase 2 ENACT clinical trial using a dose of 2.60 mg/kg in patients undergoing endovascular repair of brain aneurysms, both unruptured and ruptured, the data suggest a treatment effect of nerinetide on the procedurally – induced strokes. The treatment effect was most evident when evaluating lesion counts using DWI or FLAIR imaging, and also in exploratory analyses when evaluating lesion volume in the mITT population. The treatment effect was most pronounced in participants who suffered from a ruptured brain aneurysm, in whom infarct numbers and infarct volumes were reduced. Exploratory analyses suggested that stroke volumes were also reduced when analyses accounted for delayed strokes, or for the non-normality of the data. There were three deaths during this trial, two in the placebo group and one in the

nerinetide group. The SAEs leading to death were all severe and unrelated to study drug. There were no other discontinuations due to adverse events. Overall, nerinetide (NA-1) 2.60 mg/kg was well-tolerated and no safety concerns were identified in any of the patient groups in the trial.

The selection of the single IV dose of 2.60 mg/kg is based on the safety and tolerability profile of nerinetide observed in the Phase 1 and 2 clinical trials.

In the ESCAPE-NA1 trial, treatment with single 2.6 mg/kg IV dose of nerinetide did not achieve the primary endpoint of the trial in all participants with ischemic stroke due to large vessel occlusion and who were selected for EVT, with and without intravenous alteplase. Among participants who were not treated with alteplase, a treatment effect was observed. Specifically, there was a benefit in the nerinetide group on the proportion of participants achieving an mRS 0-2 at 90 days (59.4% for nerinetide participants vs. 49.8% for placebo participants) (Odds Ratio = 1.657; 95% CI 1.055, 2.603; p = 0.028). There was also a reduction in mortality rate in the participants receiving nerinetide with an absolute reduction in mortality rate of 7.5% (relative difference of 39.7%; p = 0.041, Fisher's Exact Test) without an increase in severe disability (i.e., mRS 4 or 5). Other measures of function, including the NIHSS and BI trended in the same direction, in favor of nerinetide. Lastly, treatment with nerinetide resulted in a significant reduction in median infarct volumes in the nerinetide group (p = 0.048).

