4.2 Estimands

Death is an intercurrent event which may occur during the study. The fact that a participant has died may in itself be informative for quantifying the treatment effect, although data collections after death will not exist. Therefore, the primary and secondary estimands will be focusing on the composite strategy. More specifically, death will be incorporated as part of the primary and secondary estimands as described below and in Section 4.3.

The primary estimand will be the difference in the mRS response (i.e., mRS score of 0-2) proportions between treatment conditions (nerinetide vs. placebo) in the target patient population at Day 90. Deaths occurring over the Day 90 period will be considered as non-response.

The secondary estimands are defined below:

- The difference in mortality rate over the 90-day period between treatment conditions in the target patient population.
- The difference in worsening of stroke proportions between treatment conditions in the

target patient population over the 90-day period. Death meets the definition of worsening of stroke.

- The difference in showing a shift in mRS categories between treatment conditions in the target patient population at Day 90. Death occurring prior to Day 90 will be assigned with the worst mRS score (score of 6).
- The difference in NIHSS response (i.e., score of 0-2) proportions between treatment conditions in the target patient population at Day 90. Death occurring prior to Day 90 will be considered as non-response.

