4.3 Missing Data

Every effort will be made to keep missing data, particularly the Day 90 outcome assessments, to a minimum. However, some missing data may be inevitable due to, for example, loss to follow-up.

All imputed values will be determined prior to database lock and conducting primary analyses via the rules documented prospectively in this Statistical Analysis Plan for the study.

To incorporate death as part of the estimand definition following the composite strategy, deceased participant will be assigned a score 6 on the mRS, 42 on the NIHSS and 0 on Barthel Index and be counted as non-responders. In addition, deceased participants are considered as experiencing worsening of stroke. Thus, there will be no missing mRS, NIHSS, BI or worsening of stroke data due to death.

No imputation is planned for safety data. Efficacy outcomes will be imputed using a datainformed imputation as follows:

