6.6.4 EQ-5D-5L at 1 Year

The EQ-5D-5L will be obtained by telephone or in-person interview from trial participants at 1 year. EQ-5D-VAS will be analyzed and reported as described in Section 6.3.5.

Table 4: Summary of Inferential Efficacy Analyses

	Endpoint	Primary Analysis*	Sensitivity Analysis*	Supportive Analysis*
Primary	Day-90 mRS Responder (≤2 vs. >2)	Adjusted log-binomial regression model, ITT, SI Estimation of unconditional treatment effect will also be reported.	 Adjusted log-binomial regression model, ITT, OC Adjusted log-binomial regression model, ITT with Day 90 completers only (if missingness ≤ 5%) Adjusted log-binomial regression model, ITT, MI (if missingness > 5%) Adjusted log-binomial regression model, ITT, Tipping Point Analysis (if missingness > 5%) 	 Primary analysis with the interaction term added (treatment by randomization stratification factor) Adjusted log-binomial regression model, ITT, Re-randomization CMH, ITT, SI Unadjusted logistic regression, ITT, SI Adjusted log-binomial regression model, PP, OC
Secondary	Day-90 Mortality	Adjusted log-binomial regression model, ITT Missing data imputed based on Day 30 status	Adjusted log-binomial regression model, ITT, OC	 Mortality Rate: Unadjusted logistic regression, ITT, Missing data imputed based on Day 30 status Adjusted log-binomial regression model, PP, OC Time to Death (Days): Kaplan Meier, ITT, OC Cox proportional hazard regression, ITT, OC
	Worsening of Stroke	Adjusted log-binomial regression model, ITT, Missing data imputed based on Day 30 status	Adjusted log-binomial regression model, ITT, OC	 Unadjusted logistic regression, ITT, Missing data imputed based on Day 30 status Adjusted log-binomial regression model PP, OC
	Day-90 mRS shift (Ordinal)	POM, ITT, SI	POM, ITT, OCPOM, ITT with Day 90 completers only	POM, PP, OC
	Day-90 NIHSS Responder (≤2 vs. >2)	Adjusted log-binomial regression model, ITT, LOCF	Adjusted log-binomial regression model, ITT, OC	 Unadjusted logistics regression, ITT, LOCF Adjusted log-binomial regression model, PP, OC
Tertiary	Stroke volume	Linear regression, ITT, OC	N/A	Student's t-test, ITT, OC
	Day-90 Barthel Responder (<95 vs.≥95)	Adjusted log-binomial regression model, ITT, OC	N/A	N/A
	Day-90 mRS	Adjusted log-binomial	N/A	N/A

	Endpoint	Primary Analysis*	Sensitivity Analysis*	Supportive Analysis*
	Responder (≤3 vs. ≥4)	regression model, ITT, SI		
	Day-90 mRS Responder (≤1 vs. >1)	Adjusted log-binomial regression model, ITT, SI	N/A	N/A

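### EQ-VAS is compared among survivors only, with no analysis that counts deaths, so if mortality falls as expected a benefit across all randomized participants would be understated

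*Combined protocol and SAP*

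**What the plan says.** **EQ-VAS.** SAP 6.3.5: "An analysis of covariance (ANCOVA) model will be fit to the EQ-VAS endpoint with the nerinetide/placebo treatment indicator variable", adjusted for the stratification variables and covariates. SAP Table 4 specifies this ANCOVA for the ITT population on observed cases (OC), at Day 90 and at 1 year, and marks sensitivity and supportive analyses as not applicable in both rows. SAP 6.6.4 refers the 1-year analysis back to 6.3.5. SAP 6.6 refers missing 1-year data to 4.3, which has no EQ-VAS rule.

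**Deaths on the other scales.** SAP 4.3: "deceased participant will be assigned a score 6 on the mRS, 42 on the NIHSS and 0 on Barthel Index". It concludes: "Thus, there will be no missing mRS, NIHSS, BI or worsening of stroke data due to death". EQ-VAS and stroke volume are not in that list. SAP 4.2 says that "the primary and secondary estimands will be focusing on the composite strategy", and the secondary estimands it lists are the four Day 90 ones.

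**Stroke volume.** Table 4 gives "Linear regression, ITT, OC", with a t-test, also on observed cases, in support. SAP 3.5 times the scan at 18 to 56 hours after randomization. For worsening of stroke, SAP 6.2.2 adds a supportive analysis to take in "any cases in which the stroke worsened so rapidly that the patient was deemed palliative early on and did not undergo further imaging".

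**Status.** SAP 6.3 treats the tertiary analyses as exploratory and outside the fixed sequence. Protocol Table 9-1 has EQ-5D-5L summarized descriptively only. The SAP adds the ANCOVA, and protocol 9.3 gives the SAP precedence. At 1 year, EQ-5D-5L is a secondary outcome of a sub-study meant to support the Day 90 results.

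**The concern.** The OC label alone does not remove deaths. Barthel is also OC in Table 4, yet SAP 4.3 gives its deaths a score of 0. What removes deaths from EQ-VAS is that they have no value on it. The ANCOVA is then restricted by an event that follows randomization and that the drug is hoped to change: reducing mortality is the first secondary objective. Baseline covariates do not undo that selection.

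If nerinetide keeps alive some patients who would have died on placebo, and their quality of life is below that of other survivors, they enter the nerinetide mean with no counterpart in the placebo mean. The observed-case difference moves against the drug, and the gain from being alive is not counted. At 1 year the asymmetry is sharper. SAP 6.6 has the interviewer estimate outcomes for contacted survivors who cannot complete the interview, so severely impaired survivors are kept and the dead are left out.

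At stake is how the quality-of-life objectives at Day 90 and 1 year are read, not the primary conclusion.

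**Working it through.** **What can be reproduced.** The documents give no power, SD or expected effect for EQ-VAS or stroke volume. The only design figure used here is the protocol's 850 evaluable participants at 1:1, or 425 per arm. Its stated power of 91.3% is reproduced to within a point with the protocol's two boundaries: 90.6% for 0.5 against 0.6114, and 91.8% for 0.5 against 0.614. The SAP still plans an initial 680; that changes the counts below but not the percentages.

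**Inputs** (protocol 2.1.5, prior trial, participants without alteplase): "an absolute reduction in mortality rate of 7.5" percentage points; relative difference 39.7%; mRS 0-2 in 59.4% against 49.8%.

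**Step 1. Deaths by arm.**
- Placebo mortality = 0.075/0.397 = 18.9%; nerinetide = 18.9 − 7.5 = 11.4%.
- At 425 per arm: about 80 and 48 deaths, leaving about 345 and 377 survivors. At 340 per arm (680 in total): 340 × 0.189 = 64 and 340 × 0.114 = 39 deaths.

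**Step 2. Function among survivors.**
- mRS 0-2 among survivors: 59.4/88.6 = 67.0% against 49.8/81.1 = 61.4%.
- mRS 3-5 among all participants: 88.6 − 59.4 = 29.2% against 81.1 − 49.8 = 31.3%.

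**Step 3. EQ-VAS difference on the prior trial's figures.** Assume EQ-VAS depends only on mRS group, with mean *h* for mRS 0-2 and *l* for mRS 3-5. The documents give neither, so a range is shown.
- Observed cases: (0.670 − 0.614) × (*h* − *l*).
- Deaths scored 0: (0.594 − 0.498) × *h* + (0.292 − 0.313) × *l*.

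| *h*, *l* | Observed cases | Deaths = 0 | Share lost |
|---|---|---|---|
| 80, 40 | +2.25 | +6.84 | 67% |
| 78, 50 | +1.58 | +6.44 | 75% |
| 75, 55 | +1.13 | +6.05 | 81% |
| 80, 60 | +1.13 | +6.42 | 82% |

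(Computed with unrounded proportions.)

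**Step 4. When the sign would reverse.** Under the same assumption, the observed-case difference is zero when mRS 0-2 among survivors is equal in the two arms. That needs a nerinetide rate of 0.498 × 0.886/0.811 = 54.4%, a gain of 4.6 points alongside the full mortality reduction. The prior trial's gain was 9.6 points, and protocol 9.1 plans for about 11.

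The limiting case is a survival benefit with no other effect. Assume that no patient is harmed into death. The extra survivors are then 7.5/88.6 = 8.5% of nerinetide survivors. If other survivors average 70 in both arms and the extra survivors 50 or 30, the observed-case difference is −0.085 × 20 = −1.7 or −0.085 × 40 = −3.4. With deaths scored 0 it is 0.075 × 50 = +3.8 or 0.075 × 30 = +2.3. With an assumed SD of 20, the standard error of the observed-case difference is 20 × √(1/345 + 1/377) = 1.5.

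**Step 5. Stroke volume.** Only participants who die or are made palliative before the 18-56 hour scan lose their volume; later deaths keep one. The 90-day mortality figures therefore do not measure this loss, and the documents give no count, so no size can be computed.

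**The case against.** A reader might infer that the plan would make a life-saving drug appear to harm quality of life. The documents do not support that as the expected result. It requires a survival benefit with little functional gain, whereas the trial that supplies the mortality figure also reports better function, and its mRS 3-5 share is slightly lower on nerinetide. That objection stands.

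A reader might also take stroke volume to have the same fault on the same scale. It does not. The scan is early, CT may replace MRI, and SAP 6.2.2 speaks of patients who had no *further* imaging, which does not establish that they lacked the Day 2/3 scan. If the largest placebo infarcts were lost, the error would understate a benefit. This also stands.

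Scoring death as 0 is a choice of estimand. It turns a quality-of-life scale partly into a mortality measure; in the limiting case of step 4 the whole positive difference is survival, which mortality and the mRS analyses already capture. A survivor comparison, named as such, is legitimate. This stands against making the death-inclusive analysis the sole main one, but not against reporting both.

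Finally, the OC label is disclosed, deaths by arm are reported as a secondary endpoint, and the 1-year report tabulates deaths and losses. This helps an alert reader, but no planned analysis joins these deaths to the EQ-VAS result.

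**Conclusion.** The point holds for EQ-VAS. As written, the Day 90 and 1-year comparisons are among survivors, although SAP 4.3 counts death as the worst outcome on three other scales and a mortality difference is expected. On the prior trial's figures the difference is about +1 to +2 points in observed cases, against about +6 to +7 with deaths scored 0. Two thirds or more of the all-participant difference is not seen, though part of that difference is mortality itself.

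The size rests on the prior trial's mortality and mRS 0-2 rates recurring, on the assumed EQ-VAS means, and on EQ-VAS depending only on mRS 0-2 against 3-5. No 1-year mortality is given, so the 1-year size is unknown.

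It would be too strong to say that the quality-of-life objective cannot be answered, or that any confirmatory result is at risk. Day 90 EQ-VAS is exploratory, the 1-year outcome belongs to a supportive sub-study, and the alpha-controlled endpoints all count death. For stroke volume the bias is possible, of unknown size and probably smaller.

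**What to change.** **EQ-VAS** (SAP 4.3, 6.3.5, 6.6.4 and Table 4):
- Add an analysis of all randomized participants (at 1 year, of the sub-study population) in which those dead by the visit are scored 0, or ranked worst, consistent with Barthel. State whether this covers documented deaths only or also those imputed as dead under SAP 4.3.1.
- Report it beside the observed-case ANCOVA. Label that ANCOVA as a survivor analysis and show deaths by arm in the same table.

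**Stroke volume** (SAP 6.3.1 and Table 4), as a lesser point: add a worst-rank sensitivity analysis for participants who died or were palliated before the 18-56 hour scan, and report the number without imaging by arm and reason.

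**Cost.** SAP wording and a few table columns; vital status is already collected at every visit. The death-inclusive EQ-VAS has a spike at 0 and partly reflects mortality, so its mean is harder to read and should not be shown without the survivor result.
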